## **9.2 Procedure for Patient Premature Discontinuation**

In case of premature discontinuation and whenever possible, Investigators will ask patients to perform Visit #5 (Exit Visit) as the Premature Discontinuation Visit. At the end of the Exit Visit, the Investigator will declare premature discontinuation in the eCRF. If study participation is terminated due to an AE possibly related to the study treatment or trial-related procedures, the patient will however be followed by additional examinations according to the medical judgment of the Investigator until the AE is resolved or the Investigator deems further observations or examinations to be no longer medically indicated. All collected data should be recorded in the source documents and eCRF.

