**Test Product Strength and Mode of Administration:**

*Test Product:* 3 different strengths of JTA-004 (JTA-004 50 (2ml), JTA-004 100 (2ml) and JTA-004 50 (4ml) and one reference will be tested. All patients will be treated by a single intra-articular administration at visit #2.

**Study Visits:** There will be 5 visits defined as follows:

- Screening visit (Visit #1)
- Baseline/Treatment visit (Visit #2)
- Follow-up visits at 2 weeks (Visit #3), 3 months (visit #4) and 6 months (visit #5)

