**JTA-KOA1 - Clinical Study Protocol**

JTA-KOA1-CSP

V 04

Author: EB

Date: May 10, 2017

Pg. 46/114

During Visit #2, the following procedures will be performed:

- | [REDACTED]
- | [REDACTED]
- | [REDACTED]
- | [REDACTED]
- | [REDACTED]
- | [REDACTED]
- | [REDACTED]
- | [REDACTED]
- | [REDACTED]
- | [REDACTED]
- | [REDACTED]
- | [REDACTED]
- | [REDACTED]
- | [REDACTED]
- | [REDACTED]

During the whole study follow-up after IA of JTA or reference product, patients must not receive any IA treatment in the target knee (either hyaluronic acid or corticoids injection). If such IA injection is performed, reasons must be documented in the concomitant medications section and the patient must be withdrawn from study. The “Early Termination Form” must be completed in such case.

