**Table 2: Administration of the Investigational medicinal product**

	JTA-004	Reference
Product	JTA-004 50 & 100	Synvisc-One®
Route of administration	(Percutaneous) intra-articular administration	(Percutaneous) intra-articular administration
Single dose	2 or 4 ml	6 ml
Dosage schedule	One single dose per patient on Study Day 0 (Visit #2)	One single dose per patient on Study Day 0 (Visit #2)

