### 6.2.4 Concomitant Medications

Throughout the clinical trial, the Investigator may prescribe any concomitant medications or treatments deemed necessary to provide adequate supportive care except for those listed in the exclusion criteria. If they are required, the patient will have to be withdrawn from the study.

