**9 PREMATURE REMOVAL FROM THE STUDY****9.1 Reasons for Patient Premature Discontinuation**

Notification of patient study discontinuation (and reasons for discontinuation) will be communicated to the Monitor and/or the Sponsor by the Investigator as soon as possible. The Investigator will document the circumstances for premature discontinuation in the patient's eCRF as follows:

- ***Violation of eligibility criteria***

Patients will be withdrawn if incorrectly included (i.e., not in compliance with one or more eligibility criteria). The Investigator may contact the Monitor in order to discuss the potential continuation of wrongly included patients if judged that it is in the interest of the patient to continue the study.

In any case, and especially if the patient is withdrawn for safety reasons, the explanation for this discontinuation due to violation of eligibility criteria should be documented in the eCRF.

- ***Adverse Events / Serious Adverse Events***

Any patients may be withdrawn from the study at the Investigator's discretion in case of a safety concern. However, patients can be withdrawn from the study for AE/SAE (including notably clinical and/or laboratory events) only if the Investigator has clearly determined that the patient's withdrawal would reduce safety risks. In this case, the AE Page in the eCRF must be completed, explaining the rationale for withdrawal. In addition, the Investigator should ensure that adequate medical care and management will be provided to the patient.

- ***Withdrawn consent***

Participation in the study is strictly voluntary. A patient has the right to withdraw from the study at any time, and for any reason, without prejudice to further treatment, care, and patient-physician relationship. Under these circumstances, an adequate standard of care will always be adopted by the Investigator. The reason(s) for withdrawing consent will also be reviewed with the patient and documented in source documentation and the eCRF. Particularly, the patient must be carefully questioned for the possible occurrence of any AE/SAE.

JTA-KOA1 - Clinical Study Protocol				
JTA-KOA1-CSP	V 04	Author: EB	Date: May 10, 2017	Pg. 74/114

- ***Lack of compliance to the protocol***

The Investigator or the Sponsor can terminate the study at any time for non-compliant patients.

- ***Lost to follow-up***

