Efforts must be made to re-contact patients who do not return for scheduled visits in order to, at minimum, determine health status and the potential occurrence of AE/SAE. All efforts to re-contact patients will be documented in the source documentation and the eCRF.

- ***Lack of efficacy***

Early discontinuation for lack of efficacy will not be considered as an AE but as a treatment failure. The reason of the lack of efficacy will be documented in the eCRF and source documents.

- ***Other reasons***

If no above-mentioned reasons are applicable in case of early discontinuation, the other reason(s) will be clearly documented and explained in the eCRF and source documents.

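### Treated patients are withdrawn from the study after a one-time injection, and no visible text asks for their WOMAC pain score at the scheduled Month 6 date

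*Combined protocol and SAP*

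**What the plan says.** **Treatment.** The synopsis states: "All patients will be treated by a single intra-articular administration at visit #2". Table 2 gives the same single Day 0 administration for JTA-004 and for the reference.

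**Withdrawal rules.**
- Section 4.2 bars further intra-articular treatment of the target knee during follow-up. If it happens, "reasons must be documented in the concomitant medications section and the patient must be withdrawn from study".
- Section 6.2.4, on treatments listed in the exclusion criteria: "If they are required, the patient will have to be withdrawn from the study".
- Section 9.1: "Patients will be withdrawn if incorrectly included". This is weaker than the other two. The Investigator may discuss continuation with the Monitor, and the text does not say whether it applies before or after the injection.

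**What is collected at and after withdrawal.**
- Section 9.2 says that, where possible, "Investigators will ask patients to perform Visit #5 (Exit Visit) as the Premature Discontinuation Visit". Discontinuation is then declared in the eCRF.
- The only later follow-up named in 9.2 is for an adverse event possibly related to treatment or trial procedures: "the patient will however be followed by additional examinations according to the medical judgment of the Investigator until the AE is resolved".
- Section 9.1, on loss to follow-up: "Efforts must be made to re-contact patients who do not return for scheduled visits in order to, at minimum, determine health status", together with any adverse events. WOMAC is not named.

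**What the analysis needs.** The primary endpoint is the change in WOMAC pain from baseline to Month 6 (3.2.1). The FAS, which is every randomised and treated patient, is the primary cohort for superiority (10.1).

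**General follow-up text.** Section 3.1 has treated patients assessed at 2 weeks, 3 months and 6 months. Section 6.3 has endpoints determined for everyone at each scheduled visit. Section 3.4.1 has WOMAC completed at each follow-up visit. None of the three mentions withdrawn patients.

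**The concern.** In a trial of repeated dosing, withdrawal at least ends exposure. Here the whole exposure is over on Day 0, so withdrawal from the study mostly removes later measurements. A treated patient can therefore belong to the primary analysis set while no visible instruction asks for the primary outcome at its scheduled time.

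Nothing visible makes up for this. Withdrawn patients are not replaced (9.3), and the per-protocol set excludes anyone without a Month 6 pain score (10.7.2).

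Some of these exits are probably tied to pain, for example another injection in the same knee. Others need not be, such as an eligibility error or an excluded anti-hypertensive drug. If exits related to pain differ between arms, the comparison can be distorted in a way that a larger sample does not repair. A score not collected at Month 6 cannot be obtained afterwards, whereas a collected score can still be set aside in a sensitivity analysis.

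**Working it through.** **1. The passages side by side**

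| Question | Visible text | Answer |
|---|---|---|
| Does withdrawal stop study treatment? | Synopsis, Table 2 | No, it was given once on Day 0 |
| Is withdrawal from the study prescribed? | 4.2, 6.2.4 | Yes |
| | 9.1, eligibility | Default, with a route to continue and no timing stated |
| Is a score expected at exit? | 9.2 with 3.4.1 | Yes, if the exit visit takes place |
| Is a score requested at the scheduled Month 6 date after withdrawal? | 9.1, 9.2 | Not in visible text |
| Does the patient stay in the primary set? | 10.1 | Yes |

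An exit that falls inside the Month 6 window (± 4 weeks, from the contents entry for 4.5) would itself supply a Month 6 score. The gap concerns earlier exits.

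**2. The plan's own sample size**

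Inputs from 10.9: difference 7 mm, SD 10.5 mm, two-sided 0.05, power 80%, drop-out 10%. (The synopsis gives an SD of 10 mm; 10.5 mm is used here because the stated sample size rests on it.)

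- The two-sample t-test needs 36.3 per group, rounded up to 37, as stated.
- With drop-out: 37 × 1.10 = 40.7, or 37 / 0.90 = 41.1. The plan's 41 is consistent to the nearest patient, and 4 × 41 = 164.
- Expected loss from all causes: 41 − 37 = 4 per group (4/41 = 9.8%).

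**3. Precision that could be regained**

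Let k be the number per group whose Month 6 score is lost only because of the withdrawal rules. The 4 also include withdrawn consent and true loss to follow-up, so k is unknown, from 0 to 4. Standard error = 10.5 × √(2/(37 + k)); power is from the t-test.

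| k | n per group | Standard error (mm) | Power |
|---|---|---|---|
| 0 | 37 | 2.44 | 80.8% |
| 1 | 38 | 2.41 | 81.8% |
| 2 | 39 | 2.38 | 82.8% |
| 4 | 41 | 2.32 | 84.7% |

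**4. Bias, as illustration only**

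Assume that such patients are left out of the analysis and that their change is worse than that of the others by d mm. The documents give no value for d, so 5, 10 and 20 mm are shown; 10 mm is the clinically important difference cited in 10.9. With m₁ and m₂ such patients in the two arms:

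Shift in the treatment difference = (m₁ − m₂)/41 × d

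- Equal numbers in both arms: 0 mm.
- One extra patient in one arm: 5/41 = 0.12 mm, 10/41 = 0.24 mm, 20/41 = 0.49 mm. Against the assumed 7 mm, these are 1.7%, 3.5% and 7.0%.

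If exit scores are used, the shift could be smaller or nil.

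**The case against.** The strongest objection is that this is an absence in a heavily redacted text. Table 1, the procedures in 4.4 and 4.5, and section 10.10 on missing values cannot be read, and text that cannot be seen is not thereby missing from the plan. LOCF and WOCF stand in the abbreviation list but are used nowhere visible, which suggests that an imputation rule may exist. Sections 3.1 and 6.3 can be read as following every treated patient for six months. This limits the point but does not remove it. The withdrawal rules and section 9.2 are legible, the general statements do not say that assessments go on after withdrawal, and imputation does not replace a collected score.

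Second, the numbers are small, and the 10% allowance already covers planned loss for power. That stands for precision. The allowance does not address bias, but the documents also give no frequency for these withdrawals.

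Third, a Month 6 score after another injection reflects both treatments, so whether to use it is an estimand choice. That is right, but the choice is separate from whether to collect the score.

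Fourth, a blanket rule to continue visits would cut across section 9.1, where a patient may be withdrawn because this would reduce safety risks. That stands, and the fix makes an exception for it.

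Fifth, part of the record exists already: 4.2 has an Early Termination Form, and 11.1 keeps visit and exit dates, so the study day of an exit can be worked out.

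**Conclusion.** The point holds in a limited form. Visible rules require some treated patients to leave the study, and no visible text asks for their WOMAC pain score at the scheduled Month 6 date, although they stay in the primary analysis set. It is worth correcting because the correction is cheap, not because a large effect has been shown. Power would move from 80.8% to between 80.8% and 84.7%, assuming an SD of 10.5 mm, a difference of 7 mm and 0 to 4 recoverable patients per group. The bias figures rest wholly on assumed values.

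A reader might infer more, and the documents do not support it:
- That the result will be biased, or biased towards JTA-004. Neither size nor direction can be derived.
- That withdrawn patients yield no outcome at all. An exit WOMAC score is to be expected under 9.2 and 3.4.1.
- That early exit scores will pass as Month 6 scores, or that missing values have no handling rule. The relevant text is not visible.
- That every incorrectly included patient must leave after injection. Section 9.1 allows continuation and sets no timing.
- That the sample size is wrong. It reproduces.

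**What to change.** - In 4.2, 6.2.4, the eligibility item of 9.1, and 9.2, separate the protocol event from the end of data collection. For treated patients, continue WOMAC pain at the visits already scheduled up to Month 6, unless the patient withdraws consent or the Investigator judges that continued participation poses a safety risk. Flag the event in the eCRF.
- Label an early exit as an early-termination visit. Count its score as Month 6 only if it falls inside the ± 4 week window.
- Reconcile 3.1 and 6.3 with 4.2, 6.2.4 and 9.2 by stating whether the general follow-up includes patients with such an event.
- In the SAP, if it does not already do so, state whether scores after another intra-articular injection enter the primary analysis, with the alternative as a sensitivity analysis.

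Which treatments are permitted or prohibited stays as written.

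Cost: a protocol amendment with the approvals described in 11.9, possibly a revised consent form, an eCRF flag and visit label, and a few already scheduled visits for patients who would otherwise have left.

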## **9.3 Replacement of Patients**

As evaluation of the patient number to be randomised in the study takes into account a percentage of discontinued patients, patients withdrawn from the study will not be replaced.

**JTA-KOA1 - Clinical Study Protocol**

JTA-KOA1-CSP	V 04	Author: EB	Date: May 10, 2017	Pg. 75/114
--------------	------	------------	--------------------	------------

**9.4 Premature Termination of the Clinical Trial**

Overall, the study can be prematurely interrupted in certain circumstances. The Sponsor has the right to stop or interrupt the study for the following reasons:

- Safety issues
- Following a decision of the Sponsor
- Following a decision of the Agencies or the ECs

For the first three options, the ECs and Agencies must be informed.

**JTA-KOA1 - Clinical Study Protocol**

JTA-KOA1-CSP

V 04

Author: EB

Date: May 10, 2017

Pg. 76/114

**10 STATISTICAL CONSIDERATIONS AND METHODS OF ANALYSIS****10.1 Analysis Populations**

Four treatment groups including the reference and JTA-004 groups will be studied and compared. Comparisons with respect to reference will be performed in a superiority design.

Patient populations are defined as followed:

- The safety set (SAF) will include all treated patients.
- The Full Analysis Set (FAS) will include all randomised and treated patients.
- The Per-Protocol (PP) set will include all patients of the FAS without any major protocol deviation.

Demographics, baseline characteristics and efficacy variables will be analysed using the FAS. These analyses will be performed as randomised and treated.

The FAS will be considered as primary cohort for the selection of the best JTA-004 product and for the superiority analysis. Primary criterion and corresponding variables will be analysed in the FAS and in the PP.

All safety variables will be analysed on an as-treated basis using the SAF.

**10.2 Study Objectives**

Primary study objectives are (i) the selection of the best JTA-004 strength and (ii) the superiority assessment of the best JTA-004 strength efficacy to the reference. They will be determined as follow:

**JTA-KOA1 - Clinical Study Protocol**

JTA-KOA1-CSP

V 04

Author: EB

Date: May 10, 2017

Pg. 78/114

**10.6 Safety**

From inclusion (signing of ICF) to the end of the study follow up at Month 6, patients will be systematically assessed for the potential occurrence of any (serious) product or procedure related adverse events using patient open questionnaire, physical examination and laboratory measurements.

Safety will be assessed using the following variables:

- AE and SAE
- Vital signs and physical examination
- Laboratory analyses
- Concomitant medications

The final Study Report, including assessment of both safety and efficacy endpoints, will be established at Month 6.

**10.7 Statistical Analysis**

Continuous variables will be described using the number of observed values, mean, standard deviation (SD), median, first quartile, third quartile, minimum and maximum values.

Categorical data will be presented using counts (number and number of non-missing data) and percentages.

All tests will be conducted at a 5% two-sided alpha level of significance unless otherwise stated.

**10.7.1 *Patients Dispositions***

All enrolled patients will be accounted for. All post-inclusion discontinuations will be summarised by time of, and reason for, discontinuation. The number of patients screened and not included will be presented with the main reason for their non-inclusion.

Patient disposition will be based on the screened population and tabulated for the following categories:

- Total number of patients enrolled

**JTA-KOA1 - Clinical Study Protocol**

JTA-KOA1-CSP

V 04

Author: EB

Date: May 10, 2017

Pg. 79/114

- Number (percentage) of patients completing the study
- Number (percentage) of patients prematurely discontinued from study
- Primary reason for premature discontinuation
- Number of patients in the SAF
- Number of patients in the FAS
- Number of patients in the PP

For each population, reasons for exclusion from the population will be carefully described.

#### 10.7.2 Protocol Deviations

Patients presenting major deviation will be excluded from the PP. Major protocol deviations will be as follows:

- Violation of inclusion/exclusion criteria
- Missing WOMAC® subscale A score at baseline and/or at Month 6

Major and minor protocol violation will be precisely defined. Frequency and percentages of patients with protocol deviations will be tabulated.

#### 10.7.3 Demographics and other Baseline Characteristics

Descriptive statistics of demographics, and other baseline characteristics as well as medical history will be presented for all included patients. In addition, a summary of demographic and baseline characteristics will be presented by Investigation Site.

#### 10.7.4 Medical History, Concomitant Medications

Previous and concomitant medications will be summarised for all enrolled patients.

Frequency of medication will be summarised using descriptive statistics:

- frequency of patients with at least one previous medication
- frequency of patients with at least one concomitant medication

**JTA-KOA1 - Clinical Study Protocol**

JTA-KOA1-CSP

V 04

Author: EB

Date: May 10, 2017

Pg. 80/114

Frequency will be given by preferred term according to the WHO Drug Dictionary (WHO DD) used for drugs coding. Each frequency table will be sorted by descending frequency of ATC term and then within each ATC by descending frequency of WHO Drug name (all treatment groups). Medical history will be summarised for all included patients, and frequency of pathologies will be summarised using descriptive statistics. Frequencies will be given by system organ and preferred term according to the MedDRA Dictionary.

#### 10.7.5 Primary Endpoint

The mean change in the WOMAC® VA3.1 pain subscale score of JTA-004-treated patients between baseline and Month 6 will be compared to the mean change in the WOMAC® VA3.1 pain subscale score of the reference-treated patients between baseline and Month 6.

The following hypothesis is stated to show superiority of JTA-004 to Reference:

H0: The difference in the mean change from baseline at Month 6 between JTA-004 and Reference is superior or equal to 0.

H1: The difference in the mean change from baseline at Month 6 between JTA-004 and Reference is inferior to 0.

This hypothesis is expressed mathematically by:

H0: MeanJTA-004 - MeanReference ≥ 0 versus

H1: MeanJTA-004 - MeanReference < 0

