**JTA- KOA1 - Clinical Study Protocol**

JTA-KOA1-CSP

V 04

Author: EB

Date: May 10, 2017

Pg. 8/114

*Primary Endpoint*

The primary endpoint is the change between baseline and Month 6 of the Western Ontario and McMaster Universities (WOMAC® VA3.1 pain subscale (subscale A).

Primary study objectives are (i) the selection of the best JTA-004 strength and (ii) superiority assessment of the best JTA-004 strength efficacy to the reference or (iii) stop the trial at interim analysis for futility. They will be determined as follow:

- For selection of best JTA-004 strength, by comparing the different JTA-004 strengths to the reference with respect to the WOMAC® VA3.1 pain subscale score (mean differences between baseline and Month 3)
- For superiority assessment, by comparing the best JTA-004 strength and reference on the mean differences in WOMAC® VA3.1 pain subscale score between baseline and Month 6, assuming a mean between group difference of 7 mm in favor of the best JTA-004 strength (i.e., difference JTA-004 minus Reference of -7 mm) with a standard deviation of 10 mm.

The following hypothesis is stated to show superiority of JTA-004 to Reference:

- H0: The difference in the mean change from baseline at Month 6 between JTA-004 and Reference is superior or equal to 0.
- H1: The difference in the mean change from baseline at Month 6 between JTA-004 and Reference is inferior to 0.

The secondary efficacy endpoints are:

- WOMAC® VA3.1 pain subscale (WOMAC® subscale A) at Month 3
- WOMAC® VA3.1 total score over the time

*Safety Analysis*

All safety analyses will be conducted on the safety population and tabulated by treatment group.

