#### 3.2.1 Primary Endpoint

The primary endpoint is the Western Ontario and McMaster Universities (WOMAC® VA3.1 pain subscale (subscale A): the individual changes in WOMAC® VA3.1 pain subscale score between baseline and Month 6 will be calculated and compared to the reference group.

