#### 10.7.6 Secondary ██████████ Endpoints

For the analysis of the secondary endpoints,

- WOMAC® VA3.1 pain subscale (WOMAC® subscale A) at Month 3
- WOMAC® VA3.1 total score over time

groups will be compared using a parametric or non-parametric ANCOVA (according to the normality of data and the homogeneity of the variances) with the following factors: baseline value and group. Repeated measures analyses will be performed on longitudinal data.

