### 10.9 Sample Size Estimation

The sample size calculation for the superiority trial for the primary endpoint – change in WOMAC® VA3.1 pain subscale from baseline to Month 6 - is based the following assumptions:

- The mean pain difference of patients treated with the JTA-004 and those treated with the reference treatment is assumed to be -7 mm (i.e. the mean JTA-004 treatment is 7 mm better than the reference). The absolute mean difference is set to 7 mm which is below the accepted MCID of the WOMAC® VA3.1 pain subscale, which is 10 mm (Ehrich *et al.*, 2000; Bellamy *et al.*, 2001);
- The standard deviation of the mean pain difference between the two treatments, estimated from the Borrás-Verdera *et al.*, 2012 and Pavelka and Uebelhart., 2011 data, are in the range of 4.7 to 6.6 mm for sample sizes between 48 and 24, respectively. To ensure maximal power, a standard deviation value of 10.5 was used for sample size estimation.);

Under the scenario of a mean between group difference of -7 mm (i.e., JTA-004 is better than control by a mean of 7 mm) with a standard deviation of 10.5 mm, thirty-seven (37) patients per group are required for analysis, reaching a power of 80% to test for superiority, keeping the type I error at 0.05 (two-sided). This would allow collecting enough efficacy data per group while avoiding exposing too many patients.

The level of drop-out is estimated to 10%. Thus 41 patients per group have to be included.

As recruitment will continue in all 4 treatment groups until the final analysis, the maximum total number of included patients will be 164 (4 x 41).

JTA-KOA1 - Clinical Study Protocol

JTA-KOA1-CSP	V 04	Author: EB	Date: May 10, 2017	Pg. 84/114
--------------	------	------------	--------------------	------------

[REDACTED]

[REDACTED]

[REDACTED]

[REDACTED]

[REDACTED]

[REDACTED]

[REDACTED]

[REDACTED]

[REDACTED]

[REDACTED]

[REDACTED]

[REDACTED]

[REDACTED]

[REDACTED]

[REDACTED]

[REDACTED]

[REDACTED]

[REDACTED]

[REDACTED]

[REDACTED]

[REDACTED]

[REDACTED]

[REDACTED]

[REDACTED]

[REDACTED]

[REDACTED]

[REDACTED]

[REDACTED]

[REDACTED]

[REDACTED]

JTA-KOA1 - Clinical Study Protocol

JTA-KOA1-CSP	V 04	Author: EB	Date: May 10, 2017	Pg. 85/114
--------------	------	------------	--------------------	------------

[REDACTED]

[REDACTED]

[REDACTED]

[REDACTED]

[REDACTED]

[REDACTED]

[REDACTED]

[REDACTED]

[REDACTED]

[REDACTED]

[REDACTED]

[REDACTED]

[REDACTED]

[REDACTED]

[REDACTED]

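### Section 10.7.5 names no model or covariate for the primary Month 6 pain comparison, while 10.7.6 adjusts the same subscale at Month 3 for baseline

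*Combined protocol and SAP*

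**What the plan says.** Section 10.7.5 describes the primary analysis in one sentence, "The mean change in the WOMAC® VA3.1 pain subscale score of JTA-004-treated patients between baseline and Month 6 will be compared" with that of the reference-treated patients, and then sets out the hypotheses. The alternative is: "The difference in the mean change from baseline at Month 6 between JTA-004 and Reference is inferior to 0". It gives no test, model or covariate.

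Two other places are worded in the same way. Section 3.2.1 says "the individual changes in WOMAC® VA3.1 pain subscale score between baseline and Month 6 will be calculated and compared to the reference group". The synopsis describes the superiority assessment as made "by comparing the best JTA-004 strength and reference on the mean differences in" the pain subscale score to Month 6, and it describes strength selection through "mean differences between baseline and Month 3".

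Section 10.7.6 does name a method. It covers the pain subscale at Month 3 and the total score over time, using parametric or non-parametric ANCOVA "with the following factors: baseline value and group". The Month 6 primary endpoint is not on its list.

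Section 10.9 sizes the trial for a 7 mm difference with an SD of 10.5 mm at two-sided 0.05: "thirty-seven (37) patients per group are required for analysis, reaching a power of 80% to test for superiority".

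**The concern.** In the readable text, a secondary endpoint has a stated model with a baseline covariate. The confirmatory test of the same subscale has none in its own section. An analyst working from 10.7.5 alone could run a plain two-sample test of change scores, an ANCOVA, or something else, and each would fit the wording.

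If the plain test were run, nothing would be biased. The cost would be precision: a change score subtracts the whole baseline value, whereas ANCOVA subtracts the fraction that the data support. The Month 3 and Month 6 estimates of one subscale would then also rest on different models. Planned power has almost no margin above 80%, so an improvement that needs no new data is worth having.

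**Working it through.** **Inputs from the documents.** Difference 7 mm, SD 10.5 mm, two-sided alpha 0.05, 37 evaluable patients per group (section 10.9); equal allocation (section 10.8).

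**Inputs assumed.** The documents give no correlation (rho) between baseline and Month 6 pain and no visit-specific SDs. I take rho from 0.3 to 0.9 and k = baseline SD / Month 6 SD from 0.7 to 1. I also read 10.5 mm as the SD of the change score. Section 10.9 calls its source quantity the SD of the mean pain difference between the two treatments, so that reading is an assumption as well.

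**Step 1: reproduce the plan's figure.** Unadjusted two-sample t-test:
- Standard error = 10.5 × sqrt(2/37) = 2.441 mm, so the noncentrality is 7/2.441 = 2.87 on 72 df.
- Power is 79.7% at 36 per group and 80.8% at 37 per group, so 37 is the smallest n that reaches 80%. The plan's figure reproduces.
- The 95% CI half-width at 37 per group is 4.87 mm.

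**Step 2: effect of adjustment on variance.** Write s for the Month 6 SD.
- Variance of the change score = s² × (1 + k² − 2 × rho × k).
- ANCOVA residual variance = s² × (1 − rho²).
- Variance ratio, ANCOVA to change score = (1 − rho²) / (1 + k² − 2 × rho × k).

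With k = 1 the ratio is (1 + rho)/2. With rho = k it is (1 − k²)/(1 − k²) = 1, which means no gain.

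**Step 3: equal SDs (k = 1), 37 per group, 71 df.** Residual SD = 10.5 × sqrt(ratio).

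| rho | Variance ratio | Residual SD (mm) | 95% CI half-width (mm) | Power |
|---|---|---|---|---|
| 0.3 | 0.65 | 8.47 | 3.92 | 93.9% |
| 0.5 | 0.75 | 9.09 | 4.22 | 90.4% |
| 0.7 | 0.85 | 9.68 | 4.49 | 86.6% |
| 0.9 | 0.95 | 10.23 | 4.74 | 82.7% |

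**Step 4: unequal SDs.**
- k = 0.85, rho 0.3 / 0.5 / 0.7 / 0.9: power 90.4% / 86.2% / 82.4% / 81.3%. At rho = 0.85 the ratio is 1.000.
- k = 0.7, rho 0.3 / 0.5 / 0.7 / 0.9: power 86.6% / 82.7% / 80.7% / 87.5%. At rho = 0.7 the ratio is 1.000.

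**Step 5: worst case.** Estimating the covariate slope multiplies the variance by about 1 + 1/(2 × 37 − 4) = 1 + 1/70, or 1.4%. In the zero-gain cases this takes power to 80.2%, against 80.8% unadjusted, a loss of 0.6 percentage points.

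All of these are fixed two-arm calculations. Selection among three strengths and interim sample-size re-estimation are not modelled.

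**The case against.** The strongest reply is that 10.7.5 is silent rather than unadjusted. It states a contrast and its hypotheses. Under randomisation, an ANCOVA of change with baseline as covariate estimates that same difference in mean change, so the wording is compatible with adjustment. Section 3.2.1 and the synopsis define the variable rather than a model. This stands. A reader might infer that the plan has chosen an unadjusted primary test, or that 10.7.5 and 10.7.6 contradict each other. The documents support neither: one section leaves the model open and the other specifies one for different endpoints. The match between 37 per group and an unadjusted t-test shows how the trial was sized, not how it will be analysed.

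The second reply is that the method may sit in text that cannot be read. The table of contents puts 10.3 Primary Endpoint on page 77 and 10.10 and 10.11 on page 83. Section 10.2 breaks off where the determination of the objectives should follow, and pages 84 and 85 are blacked out. The reference list includes papers on adaptive Dunnett tests for treatment selection and on a sharpened Bonferroni procedure that no readable text cites. This also stands. It rules out any statement that the plan as a whole omits baseline adjustment. It does not show that a baseline covariate is stated there.

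Third, the size of the gain depends on the assumed grid. An SD ratio outside it gives other values: k = 0.5 with rho 0.9 gives a variance ratio of 0.19/0.35 = 0.54. That is fair, and the range above is illustrative rather than a bound.

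**Conclusion.** The point holds as a limited one. In the readable text, the primary Month 6 comparison has no stated model or covariate in 10.7.5, whereas the same subscale at Month 3 has ANCOVA with baseline. The comparison as described is valid and unbiased, and the sample size is correct for it. A reader might conclude that the trial is underpowered; it is not on its own inputs, since unadjusted power is 80.8%.

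What is available is a usually more precise analysis at almost no cost. Power would be about 83% to 94% at 37 per group for rho 0.9 to 0.3, given equal SDs and 10.5 mm as the SD of change. There is essentially no gain where rho equals the SD ratio, and the worst loss in the cases examined is about half a percentage point. No conclusion is drawn about page 77 or pages 83 to 85.

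**What to change.** In 10.7.5, add a sentence stating that the change in WOMAC pain from baseline to Month 6 is compared by ANCOVA with treatment group and baseline WOMAC pain, and that the adjusted difference and its confidence interval are reported. The hypotheses can stay as they are, because the adjusted difference estimates the same quantity. If a baseline-adjusted primary model is already stated on page 77 or pages 83 to 85, no change is needed.

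The cost is one sentence, with no extra data, visits or patients.
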